### **3. STUDY DESIGN**

This is a randomized, active controlled, parallel-group, open label study.

[figure not shown]
Approximately 1500 subjects will be randomized 1:1 to apixaban or usual care (parenteral heparin and/or oral anticoagulation with Vitamin K antagonist (excluding other NOACs)). Usual care will be administered as per local practice and/or approved label.

Apixaban or usual care (parenteral heparin and/or oral anticoagulation with Vitamin K antagonist (excluding other novel oral anticoagulants (NOACs))) will be administered from randomization up to 30 days following cardioversion or 90 days post randomization if cardioversion is not performed within that timeframe.

[figure not shown]
Following randomization, clinical endpoints, cardioversion details (timing, type, attempts, and rhythm status), length of in-patient hospital stay and use of image guidance will be collected during the 30 days following the cardioversion or during the 90 days post randomization if cardioversion is not performed.

A schematic diagram below (Figure 1) shows the design of the study:

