#### **6.5. Guidelines for Image Guidance (eg, TEE/TOE or CT) Suggesting Atrial Thrombus**

The investigator should follow their usual practice, and in accordance with local and national guidelines. Positive TEE/TOE or CT will be submitted for adjudication.

It is expected that in the event of imaging suggesting atrial thrombus, that any cardioversion attempt would be deferred for a minimum period of at least 3 weeks of further anticoagulation, consistent with local/national guidelines. It would also be expected that repeat imaging would take place prior to consideration of further cardioversion attempts.

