#### **9.4. Independent Adjudication**

Independent Adjudicator(s) will review and adjudicate all clinical endpoints and positive TEE/TOE or CT without awareness of treatment allocation, ie, in a blinded manner. The responsibilities and procedures followed are described in the Adjudication Charter.

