8.2.4. Analyses of Clinical Endpoints

- *Stroke.*
- *Systemic embolism.*
- *Major Bleeding.*
- *Clinically Relevant Non-Major Bleeding.*
- *All cause death.*

The following time periods will be defined for reporting clinical endpoints:

- Pre-cardioversion
- Post-cardioversion
- ALL: entire duration (include 30 days follow-up after cardioversion).

The characterization of stroke, systemic embolism and death will be done based on the adjudicated endpoints during the study (according to an intention-to-treat paradigm). Analysis of these endpoints will be based on the full analysis set.

The characterization of bleeding will be done with a focus on adjudicated major bleeding and clinically relevant non-major bleeding during the treatment period (according to a safety paradigm). Analysis of these endpoints will be based on the safety analysis set.

The clinical endpoint summaries will include descriptive statistics of individual event rates and their exact 95% confidence intervals; however exact risk ratios and corresponding p-values comparing the treatment arms will also be presented without any formal testing.

Sensitivity analysis: If the TEE/TOE or CT procedures will identify subjects with thrombus (thrombus-positive), sensitivity analyses of all clinical endpoints will be run on a dataset obtained by removing those subjects from the Full Analysis Set. The dataset from which thrombus-positive (as per investigator’s assessment) subjects were excluded will be labeled as Full Prevention-Evaluable; its complementary set of Thrombus Positive-ITT will be analyzed for the endpoints of Stroke, Systemic Embolism, and Death. Sensitivity analyses of bleeding events will also be run on a dataset (labeled as Safety Prevention-Evaluable Analysis Set) obtained by removing subjects with thrombus (as per investigator’s assessment) from Safety analysis set; its complementary set of Thrombus Positive-Safety will be analyzed for the bleeding endpoints.

The Modified Full Analysis set will be analyzed for the endpoints of Stroke, Systemic Embolism, and Death.

Subgroup analyses: Clinical endpoints and safety (AEs, SAEs) will be reported for each subgroup of interest. Subgroups of interest are (please note that bleeding endpoints are based on the safety analysis set while the others are based on the full analysis set):

- “Early Cardioversion” (defined as cardioversion that occurs within 7 days from randomization),
- Image Guidance (TEE/TOE or CT),

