Routine hemoglobin and serum creatinine will be recorded within the CRF from Visit 1 to Visit 3. The data will be presented in listings without imputations and displaying even multiple findings per visit. The lab data will not be summarized.

Compliance for apixaban will be reported and summarized overall. The compliance formula is: $\# \text{tablets taken} / (\# \text{of days} * 2 + L)$ where $L=1$ if loading dose was given and 0 otherwise.

INR will be summarized for the usual care arm. Rosendaal's linear interpolation methodology will be used to determine the proportion of time in specified INR range and time to therapeutic range (i.e. time from randomization to the first INR greater than or equal to 2).

Time to withdrawal will be analyzed and displayed as a KM figure.

For the adjudicated TEEs, we will report the concordance/discordance between investigator's assessment and the adjudicator's assessment, without regard to treatment arm. Details of the adjudicated TEEs will be included in a listing, as well as details of the investigator's initial TEE assessment.

Demogs/baseline characteristics will be summarized for the following groups: 10 mg load vs no load, 5 mg load vs. no load, 10 mg load vs 5 mg load

Demogs/baseline characteristics will be compared for spontaneous vs. interventional cardioversion within the Apixaban arm.

Demogs/baseline characteristics will be compared for spontaneous vs. interventional cardioversion within the usual care arm.

Demogs/baseline characteristics will be compared for spontaneous vs. interventional cardioversion in the two treatment arms combined.

Demogs/baseline characteristics will be compared for electrical vs. pharmacological vs. both cardioversion within the Apixaban arm.

Demogs/baseline characteristics will be compared for electrical vs. pharmacological vs. both cardioversion within the usual care arm.

Demogs/baseline characteristics will be compared for electrical vs. pharmacological vs. both cardioversion in the two treatment arms combined.

Demogs/baseline characteristics will be compared for subjects with thrombus vs. subjects without thrombus.

The following analyses/comparisons will be performed for each of the clinical endpoints; the Full Analysis Set will be used for stroke, systemic embolism, and for death, while the safety dataset will be used for the bleeding endpoints;

for the following Apixaban groups: 10 mg load vs no load, 5 mg load vs. no load, 10 mg load vs 5 mg load

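### The planned investigator–adjudicator concordance covers positive TEE images only, pooled over arms: it gives a confirmation rate, omits CT, and cannot show whether over-calling differs by arm

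*SAP*

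**What the plan says.** **Which images are adjudicated.** Protocol 6.5: "Positive TEE/TOE or CT will be submitted for adjudication". Protocol 9.4 has the adjudicators review "all clinical endpoints and positive TEE/TOE or CT without awareness of treatment allocation". Neither section mentions negative images or a sample of them. Protocol 9.4 leaves procedures to the Adjudication Charter, which is not among the documents.

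**What is reported.** SAP 8.2.5: "For the adjudicated TEEs, we will report the concordance/discordance between" the investigator's and the adjudicator's "assessment, without regard to treatment arm". No statistic, denominator or interval is named, and CT is not mentioned. A listing is also planned: "Details of the adjudicated TEEs will be included in a listing", together with the investigator's initial TEE assessment.

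**Where the investigator's read is used.** SAP 8.2.4 builds the sensitivity sets on it: "The dataset from which thrombus-positive (as per investigator’s assessment) subjects were excluded" is the Full Prevention-Evaluable set. The safety counterpart and the thrombus-positive complements follow the same rule, and the same section takes thrombus findings from TEE/TOE or CT. SAP 5.4 places the identification at Visit 2, after randomization, and uses only the first evaluation when a subject has several.

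**Blinding.** Protocol 3: "This is a randomized, active controlled, parallel-group, open label study". The adjudicators are blinded to treatment allocation; nothing says that the local reader is.

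**The concern.** Three features limit what the summary can tell the reader.

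- **Selection.** If an image reaches the adjudicator only because the investigator called it positive, the investigator-negative row of the cross-classification is empty. Thrombi missed by the investigator cannot appear.
- **Modality.** CT positives are adjudicated and feed the thrombus sets, but the concordance sentence and the listing name TEE only.
- **Pooling.** The local read is made after randomization, by someone who may know the arm, and it decides who leaves the Prevention-Evaluable sets. If one arm's images are over-called more often, removals differ by arm because of the reading itself. A pooled figure cannot show this.

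At stake is how far a reader can trust the investigator's classification when interpreting the sensitivity analyses and the thrombus v no-thrombus comparisons in SAP 8.2.5.

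**Working it through.** The plan states no figure for concordance, so there is none to reproduce. The question is what the planned data can identify. The documents give no number imaged, number positive or confirmation rate, so every count below is an assumption.

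**1. What positives-only data identify.** Let a = both positive, b = investigator positive and adjudicator negative, c = investigator negative and adjudicator positive, d = both negative, n = a+b+c+d.

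- Observed agreement: po = (a+d)/n.
- Chance agreement: pe = [(a+b)(a+c) + (c+d)(b+d)]/n².
- Kappa = (po − pe)/(1 − pe).

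With investigator-positive images only, c = d = 0. Then po = a/(a+b) and pe = (a+b)a/(a+b)² = a/(a+b). The two are equal, so kappa is 0 whatever the data. For example, 36 of 40 confirmed gives po = pe = 0.90. The estimable quantity is a/(a+b), the confirmation rate.

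**2. How much that rate leaves open.** Assume 800 imaged, 40 investigator-positive, 36 confirmed (90%), and vary the unseen c:

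| c (missed) | full-table kappa | a/(a+c) |
|---|---|---|
| 0 | 0.945 | 1.00 |
| 8 | 0.849 | 0.82 |
| 20 | 0.735 | 0.64 |
| 40 | 0.594 | 0.47 |
| 80 | 0.418 | 0.31 |

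Check of the first row: po = 796/800 = 0.995; pe = (40×36 + 760×764)/800² = 0.9095; kappa = 0.0855/0.0905 = 0.945. With 28 of 40 confirmed (70%), kappa runs from 0.816 to 0.329 over the same values of c. With 500 imaged the ranges are 0.943 to 0.389 (90% confirmed) and 0.811 to 0.296 (70% confirmed).

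**3. What pooling hides.** Assume 40 positives, 20 per arm, with 28 confirmed (70%):

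| One arm | Other arm | Fisher p |
|---|---|---|
| 14/20 (70%) | 14/20 (70%) | 1.0 |
| 17/20 (85%) | 11/20 (55%) | 0.08 |
| 20/20 (100%) | 8/20 (40%) | 0.00005 |

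All three give the same pooled figure.

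**4. What a split by arm can and cannot show.** Treat the adjudicated read as the truth. With sensitivity Se, specificity Sp and thrombus prevalence π:

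- confirmed/positive = Se·π / [Se·π + (1−Sp)(1−π)]
- unconfirmed/imaged = (1−Sp)(1−π)

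Assume identical readers in both arms, Se = 95% and Sp = 97%:

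- π = 5%: confirmed/positive = 0.0475/(0.0475+0.0285) = 62.5%; unconfirmed/imaged = 0.03×0.95 = 2.85%.
- π = 10%: confirmed/positive = 0.095/(0.095+0.027) = 77.9%; unconfirmed/imaged = 0.03×0.90 = 2.70%.

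Prevalence alone moves the confirmation rate by 15.4 points and unconfirmed/imaged by 0.15 points. The second ratio is therefore the better indicator of over-calling, and it needs the number imaged per arm.

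**The case against.** **The plan claims little.** SAP 8.2.5 confines itself to adjudicated TEEs, names no kappa or overall-agreement statistic, and does not say that the result validates the thrombus sets. Counts of concordant and discordant reads among adjudicated images are estimable. This stands. A reader might infer that the analysis cannot measure agreement at all, or that the word concordance must be dropped. The documents support neither: the confirmation rate is a form of agreement, and the term is a matter of labelling once the denominator is stated.

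**The reader of the positive image is not named.** Protocol 6.5 and 9.4 say only that the image is positive. Investigator-positive is the natural reading, because an image must be called positive before it is submitted and the SAP sets use the investigator's assessment. The Charter might nevertheless provide for a sample of negatives. This stands as a caveat.

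**Pooling does not remove every check.** It is tempting to say that it does. But the listing gives subject-level reads, and the thrombus-positive sets should show the number of investigator-positive subjects per arm. What remains is that no by-arm summary of confirmation is planned, the listing covers TEE only, and the SAP does not say whether it shows the arm.

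**A by-arm confirmation rate does not isolate biased reading.** This also stands: imaging follows randomization and usually some exposure to different anticoagulants, so true prevalence may differ by arm. It argues for adding unconfirmed/imaged, not for pooling. Neither ratio can show differential under-calling.

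**The consequence is small.** The study is descriptive, with no hypothesis tests or decision rules (SAP 4.1, 4.2), and the main endpoint analyses use the Full and Safety Analysis Sets, which do not depend on imaging reads. This limits the weight of the point.

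**Conclusion.** The point holds in a limited form. As planned, the summary yields the share of positive TEE reads that adjudication confirms, pooled over arms. It does not estimate overall agreement, omits CT reads that feed the same analysis sets, and cannot show whether over-calling differs by arm.

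The conclusion rests on two inferences: that the images submitted are those the investigator called positive, and that an open-label investigator can know the arm when reading. The size in this trial is unknown because the documents give no imaging counts; the figures above show only how much the planned summary leaves undetermined.

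A reader might go further and conclude that the thrombus classification is biased by arm or that the trial's main results are in doubt. The documents give no evidence of the former and rule out the latter. The reach is the interpretation of the Prevention-Evaluable and Thrombus-Positive analyses and the thrombus v no-thrombus comparisons.

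**What to change.** Replace the concordance sentence in SAP 8.2.5 with one table covering TEE/TOE and CT, by randomized arm and overall, with one read per subject (the first evaluation, as in SAP 5.4):

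- number of subjects imaged;
- number investigator-positive;
- number confirmed and number unconfirmed by blinded adjudication;
- confirmed/positive and unconfirmed/imaged, each with an exact 95% confidence interval.

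Add two statements. First, agreement on negative images is not estimated, unless the Adjudication Charter provides for reading them. Second, a difference between arms in the confirmation rate may reflect thrombus prevalence as well as reading, while unconfirmed/imaged depends little on prevalence. Extend the listing to CT and show the randomized arm in it.

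**Cost:** a SAP wording change and one extra table. No additional reads are needed, and use of image guidance is already collected. The intervals will be wide if positives are few.

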### **9.1. Sample Size Determination**

The study is intended to be descriptive only. The study will enroll approximately 1500 subjects. No power calculation was performed but with a sample size of 1500 subjects, and based upon an ARISTOTLE warfarin naive cohort of subjects (the closest analogous data-set to this study design), the predicted incidence of stroke and systemic embolism within 30 days post cardioversion is approximately 0.3% (1 event on apixaban and 3 events on usual care). Similarly, the predicted event rate for major bleeding is approximately 0.45% (2 events on apixaban and 5 events on usual care).

For a study of this type, in order to adequately power for statistically significant claims, about 480 endpoints would be needed (similar to the ARISTOTLE trial). However, due to the limited relevant follow-up (30 days following cardioversion or 90 days post randomization), and a clinical estimate for event rate of approximately 1% this would require approximately 48000 subjects, which would not be a feasible study.

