2.1. Study Design

This is a randomized, active controlled, parallel-group, open label study. Approximately 1500 subjects will be randomized 1:1 to apixaban or usual care (parenteral heparin and/or oral anticoagulation with Vitamin K antagonist (excluding other novel oral anticoagulants)). Following randomization, endpoints will be collected during the 30 days following the early cardioversion or during the 90 days post randomization if cardioversion is not performed within that time frame.

A schematic diagram below (Figure 1) shows the design of the study:

Figure 1 Study Design Schematic

Figure 1 Study Design Schematic

The Schedule of Activities table provides an overview of the protocol visits and procedures. Refer to [Study Procedures](#) and [Assessments](#) sections of the protocol for detailed information on each procedure and assessment required for compliance with the protocol.

The investigator may schedule visits (unplanned visits) in addition to those listed on the schedule of activities, in order to conduct evaluations or assessments required to protect the wellbeing of the subject.

Table 1 Schedule of Activities

Procedure	Visit 1 Enrollment Screening/Randomization ^a	Visit 2 Cardioversion	Visit 3 Follow-Up (30 days post cardioversion (Visit 2) or up to 90 days following Visit 1) ±7 days
Visit Windows			
Informed Consent	X		
Obtain Alternative Contact	X		
Inclusion/Exclusion	X		
Demographics	X		
Medical History	X		
CHA ₂ DS ₂ -VASc score ^b	X		
Local Laboratory Parameters	X	X	X
Randomization	X		
Cardioversion ^c		X	
Endpoint Assessments ^d		X	X
Dispense Study Drug	X	X	
Collect Study Drug		X	X
Study Drug Compliance Check		X	X
Adverse Event Assessment		X	X

^a Screening/Randomization could occur on the same day

^b CHA₂DS₂-VASc - Congestive heart failure, hypertension, age, diabetes, stroke, vascular disease, age, sex category risk score

^c Cardioversion details (timing, type, attempts, and rhythm status) and use of image guidance

^d Endpoints: stroke, systemic embolism, major bleeding, clinically relevant non-major bleeding, all cause death, and length of in-hospital stay

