8.1.3 Analyses for Binary Endpoints

For binary endpoints, 95% exact confidence intervals of each event rate will be reported by treatment group. The relative risk (risk ratios) will also be reported. In the SAS language we will use the RELRISK with FMSCORE method option in the EXACT statement of PROC FREQ in order to provide exact unconditional confidence limits for the relative risk.

Other binary data comparisons will be made using Fisher’s exact test.

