for spontaneous vs. interventional cardioversion within the Apixaban arm.

for spontaneous vs. interventional cardioversion within the usual care arm.

for spontaneous vs. interventional cardioversion in the two treatment arms combined.

for electrical vs. pharmacological vs. both cardioversion within the Apixaban arm.

for electrical vs. pharmacological vs. both cardioversion within the usual care arm.

for electrical vs. pharmacological vs. both cardioversion in the two treatment arms combined.

for subjects with thrombus vs. subjects without thrombus.

References

N/A

APPENDICES

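### SAP 8.2.5 pools the two arms for cardioversion-type and thrombus comparisons with no stratification by arm, so an arm imbalance could carry part of a treatment effect into them

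*SAP*

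**What the plan says.** The closing list of SAP 8.2.5 opens with "The following analyses/comparisons will be performed for each of the clinical endpoints". It assigns the Full Analysis Set to stroke, systemic embolism and death, and the safety set to bleeding. Two groupings appear three times each: within apixaban, within usual care, and pooled. The pooled lines read "for spontaneous vs. interventional cardioversion in the two treatment arms combined" and "for electrical vs. pharmacological vs. both cardioversion in the two treatment arms combined". A further line, "for subjects with thrombus vs. subjects without thrombus", appears once, names no arm and has no within-arm counterpart in the list.

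No method is attached to these lines. SAP 8.1.3 offers an exact unconditional risk ratio and adds "Other binary data comparisons will be made using" Fisher's exact test; neither is described as stratified. SAP 8.1.2 adds Kaplan-Meier summaries and hazard ratios. Treatment is a term in the multivariate Cox models of SAP 6.4, but cardioversion type and thrombus are not among their covariates. Appendix 2.2, reserved for further detail on methods, is marked not applicable.

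SAP 5.3 defines the safety set as treated and counts subjects who received both treatments as apixaban. SAP 4.1 and 4.2 state that the study is descriptive, with no formal hypothesis testing and no decision rules.

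**The concern.** How a subject converts, by what route, and whether thrombus is seen at Visit 2 are all settled after randomisation, with treatment known. Preparation for cardioversion also differs by arm. Protocol 5.2.3.2 asks for a run of apixaban doses or, outside Japan, a loading dose before an image-guided procedure; Protocol 5.2.3.1 has the vitamin K antagonist individualised by INR. Time to cardioversion, and with it the opportunity for spontaneous reversion, could therefore differ by arm, although neither document gives waiting times by arm. In the bleeding analyses the as-treated rule means that randomisation does not protect the arm balance either.

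If a type group contains proportionately more of one arm, and the arms have different event rates, a pooled comparison mixes the two. A difference could then appear between spontaneous and interventional cardioversion, between electrical and pharmacological, or between thrombus and no thrombus, with no such difference in either arm. A programmer following the text would have no instruction to prevent this.

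**Working it through.** **The plan's own figures.** The documents state no figure for the pooled comparisons. The inputs come from elsewhere:

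- SAP 2.1: "Approximately 1500 subjects will be randomized 1:1 to apixaban or usual care", so about 750 per arm.
- Protocol 9.1, stroke or systemic embolism: "1 event on apixaban and 3 events on usual care". (1 + 3)/1500 = 0.27%, stated as about 0.3%.
- Protocol 9.1, major bleeding: "2 events on apixaban and 5 events on usual care". (2 + 5)/1500 = 0.47%, stated as about 0.45%.

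The implied treatment risk ratios are 1/3 = 0.33 and 2/5 = 0.40.

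**Assumptions.** Cardioversion type has no effect within either arm. The predicted events apply to all 750 subjects per arm. Interventional shares pA (apixaban) and pU (usual care) are hypothetical. Everyone else is counted as spontaneous, which simplifies matters because the subgroup list in SAP 8.2.4 also has a no-cardioversion category.

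**Formula.** With rA and rU the relative event rates and equal arms, the crude risk ratio, spontaneous v interventional, is

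[((1−pA)rA + (1−pU)rU) / (2−pA−pU)] ÷ [(pA·rA + pU·rU) / (pA+pU)]

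Major bleeding at 85% v 75%: (0.15×2 + 0.25×5)/0.40 = 3.875; (0.85×2 + 0.75×5)/1.60 = 3.406; ratio 1.14.

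| Interventional share, apixaban v usual care | Major bleeding (2 v 5) | Stroke/SE (1 v 3) |
|---|---|---|
| Equal | 1.00 | 1.00 |
| 85% v 75% | 1.14 | 1.16 |
| 90% v 70% | 1.28 | 1.33 |
| 90% v 60% | 1.38 | 1.44 |

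The direction depends on which arm has more spontaneous conversions. Reversing the first case to 75% v 85% gives, for bleeding, (0.25×2 + 0.15×5)/0.40 = 3.125 over (0.75×2 + 0.85×5)/1.60 = 3.594, a ratio of 0.87.

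**Second parameterisation.** Let s1 and s0 be the apixaban shares in any two groups. The crude ratio is [s1·rA + (1−s1)rU] / [s0·rA + (1−s0)rU]. For stroke/SE and bleeding respectively, 60/40 gives 0.82 and 0.84, and 70/30 gives 0.67 and 0.71. Only 100/0, where group and arm coincide, gives the whole treatment effect (0.33 and 0.40).

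**Chance imbalance alone.** If type is independent of arm, simulating the arm split for groups of 300 and 1200 gives a 95% range for the crude ratio of 0.94 to 1.06 (stroke/SE) and 0.95 to 1.06 (bleeding). For 60 and 1440 the ranges are 0.87 to 1.13 and 0.89 to 1.11.

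**After stratifying by arm.** Mantel-Haenszel, bleeding, 85% v 75%: the numerator is 0.30×0.85 + 1.25×0.75 = 1.1925 and the denominator 1.70×0.15 + 3.75×0.25 = 1.1925, so the ratio is 1.00. The 60/40 and 70/30 cases also return 1.00 for both endpoints.

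**Sampling error.** At 85% v 75% the expected bleeds are 0.30 + 1.25 = 1.55 spontaneous and 1.70 + 3.75 = 5.45 interventional. SE(log RR) ≈ √(1/1.55 + 1/5.45) = 0.91, so a ratio of 1.14 has an approximate 95% interval of 0.19 to 6.8. For stroke/SE (0.9 and 3.1 events) it is about 0.11 to 12. These normal approximations are rough at such counts and serve only to show scale.

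**The case against.** The strongest reply is that the SAP already supplies the safeguard. For both cardioversion groupings the within-arm comparisons stand beside the pooled ones and cannot be confounded by arm. A reader who sees ratios near 1 in each arm and 1.14 in the pool can work out why. This largely stands for interpretation, but it does not correct the pooled number. For thrombus, SAP 8.2.4 analyses the thrombus-positive and prevention-evaluable sets separately, so rates by arm and thrombus status should be recoverable. A direct within-arm thrombus contrast is still not listed.

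A reader might infer that any treatment effect will show up as an effect of cardioversion type. The documents do not support that. Bias needs both a treatment effect and a different mix by arm; it is nil at equal shares and partial short of complete overlap. Nor does the SAP label the thrombus line as combining the arms: pooling is inferred because no arm is named. Likewise, an unstratified analysis follows from the methods named and the silence on stratification, not from an explicit statement.

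It is also fair to say that the shares above are assumptions, that the formula ignores subjects with no cardioversion, and that the bias is small against the noise. Finally, these are exploratory items in a descriptive study, and no conclusion about apixaban rests on them. All of this stands and limits the weight of the point.

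**Conclusion.** The point holds as a minor gap. As written, the pooled comparisons by cardioversion type, and by implication the thrombus comparison, would be run without regard to arm. If group mix differs by arm, part of any treatment effect can pass into them. The illustrative size is a crude risk ratio of 1.14 to 1.44 where the within-arm ratio is 1.00. It rests on the assumed shares, the protocol's predicted events and the two-category simplification; with equal shares it vanishes.

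With about 4 stroke/SE events and 7 major bleeds predicted, sampling error will exceed this bias. Stratifying by arm would also leave confounding by patient characteristics, since neither cardioversion type nor thrombus status is randomised. The contrasts stay exploratory either way. The case for changing the text is that this particular source of confounding can be removed at almost no cost.

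**What to change.** Add to SAP 8.2.5 that every endpoint comparison pooling both arms is stratified by treatment arm: a Mantel-Haenszel or stratified exact risk ratio for binary summaries, and arm as a stratum in any Cox model. Use randomised arm for stroke, systemic embolism and death, and the as-treated grouping of the main bleeding analysis for bleeding. State that the thrombus comparison pools the arms, if that is intended, and add within-arm results for it. Present the within-arm results already planned for cardioversion type next to the stratified estimate.

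The cost is one or two sentences and a programming option; no new data are needed. With so few events a stratum may be empty or uninformative (apixaban is predicted to have a single stroke/SE event) and intervals may be slightly wider. The tables should carry a note that type and thrombus status are not randomised.
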